Protocol

Post-market, Randomized, Open-Label, Multicenter, Study to Evaluate the Effectiveness of Closed Incision Negative Pressure Therapy versus Standard of Care Dressings in Reducing Surgical Site Complications in Subjects with Revision of a Failed Total Knee Arthroplasty (PROMISES)

NCT Number

NCT03274466

Document Date

06-OCT-2018

An Acelity Company

Post-market, Randomized, Open-Label, Multicenter, Study to Evaluate the Effectiveness of Closed Incision Negative Pressure Therapy versus Standard of Care Dressings in Reducing Surgical Site Complications in Subjects with Revision of a Failed Total Knee Arthroplasty (PROMISES)	
PROTOCOL NUMBER	KCI.PREVENA.2017.01
SPONSOR	KCI USA, Inc. [name] [contact]
STUDY PRODUCTS	ActiV.A.C. [®] Therapy Unit or Prevena Plus™ 125 Therapy Unit in combination with Prevena™ Incision Dressing
ORIGINAL PROTOCOL VERSION/DATE	Version 3.0, 6-Oct-18

Confidentiality Statement: This document is a confidential communication of KCI, an Acelity Company. Acceptance of this document constitutes the agreement by the recipient that no unpublished information contained herein will be published or disclosed without the prior written approval of KCI. This document may be disclosed to appropriate Institutional Review Boards (IRBs) so long as they are requested to maintain its confidentiality.

TITLE:	Post-market, Randomized, Open-Label, Multicenter, Study to Evaluate the Effectiveness of Closed Incision Negative Pressure Therapy versus Standard of Care Dressings in Reducing Surgical Site Complications in Subjects with Revision of a Failed Total Knee Arthroplasty (PROMISES)
PROTOCOL NUMBER:	KCI.PREVENA.2017.01
TYPE AND PHASE:	Post-market, prospective, randomized, open-label
STUDY PRODUCT(S):	ActiV.A.C. [®] Therapy Unit or Prevena Plus [™] 125 Therapy Unit and Prevena [™] Dressing
STUDY OBJECTIVE(S) :	The goal of this study is to evaluate surgical site complications (SSCs) in subjects undergoing a revision of a failed total knee arthroplasty (TKA) when closed incision negative pressure therapy (ciNPT) is used to manage the closed incision, as compared to standard of care dressing.
STUDY DESIGN:	This is a post-market, prospective, randomized, open-label, multicenter, controlled study. Subjects randomized to the ciNPT treatment arm will have a Prevena [™] Dressing placed over the sutured incision immediately after surgery. Negative pressure therapy will be delivered by the ActiV.A.C. [®] or Prevena Plus [™] 125 Therapy Units up to the maximum optimal use condition specified in the Instructions for Use (IFU) document of the selected Prevena [™] Dressing but no shorter than five days post-surgery. Subjects randomized to the standard of care treatment arm will receive Aquacel [®] Ag Surgical incision dressing, or another equivalent silver-impregnated dressing, up to the maximum number of days specified in the IFU but no shorter than five days post-surgery, not inclusive of other negative pressure wound therapy devices or dressings for the duration of the study. Subjects will be regularly evaluated for SSCs through 90 days after the TKA revision.
PRIMARY ENDPOINT:	The primary endpoint is the subject incidence of Investigator-assessed surgical site complications within 90 days of TKA revision.

SECONDARY ENDPOINTS:
	
The two secondary endpoints for this study are the 90-day subject incidence of Investigator-assessed surgical site infection (superficial or deep) and the 90-day subject incidence of Investigator-assessed deep surgical site infection.

SAFETY ENDPOINT:
	
The safety endpoint is the subject incidence of adverse events.

NUMBER OF SUBJECTS PLANNED and DURATION OF PARTICIPATION:
	
The study will randomize approximately 440 subjects from approximately 15 sites in a 1:1 ratio to receive either ciNPT or standard of care after a revision TKA.
 
The duration of study participation for each subject is as follows:
 
 ○ Screening: 30 days prior to and including day of TKA revision (Day 0) ○ TKA revision ○ Treatment Period: According to the IFU document included with the selected dressing but no shorter than five days post-surgery. ○ Post Operation and Follow-up: through 90 days after TKA revision 
The maximum participation duration per subject is 134 days.

NUMBER OF STUDY SITES:
	
It is anticipated that approximately 15 study sites in North America will participate and each site will randomize and treat subjects in both treatment groups.


INCLUSION CRITERIA:
	
The subject must meet all the following inclusion criteria:
 
 ○ is at least 22 years of age on the date of informed consent ○ is able to provide their own informed consent ○ requires a TKA revision defined as one of the following: 
 ▪ a one-stage aseptic revision procedure

	
▪ a one-stage septic exchange procedure (requiring removal of all hardware) for acute postoperative infection▪ removal of cement spacer and re-implantation procedure▪ open reduction and internal fixation of peri-prosthetic fractures○ has one or more of the following:
▪ a body mass index (BMI) greater than 35 kg/m²▪ a requirement for the use of blood thinners other than acetylsalicylic acid (ASA) after surgery▪ history of or current peripheral vascular disease▪ the presence of lymphedema in the operative limb▪ insulin-dependent diabetes mellitus▪ current tobacco use or previous history of smoking and quitting within the past 30 days▪ a history of prior infection of the operative site▪ current use of immunomodulators or steroids▪ current or history of cancer or hematological malignancy (excluding localized skin cancer)▪ rheumatoid arthritis▪ current renal failure or dialysis▪ malnutrition as determined by the investigator▪ liver disease as determined by the investigator▪ status post solid organ transplant▪ HIV
--	--

	
 ○ is willing and able to return for all scheduled study visits ○ if female and of child-bearing potential, has a negative urine or serum pregnancy test at screening and day of revision surgery ○ has undergone a TKA revision resulting in a closed surgical incision

EXCLUSION CRITERIA:
	
The subject must not meet any of the following criteria:
 
 ○ is pregnant or lactating ○ will undergo a bilateral TKA within the same operative visit ○ will undergo a bilateral TKA in which the first TKA surgery is on the knee selected for study ○ will undergo a staged bilateral TKA in which the TKA revision surgery for the knee under study occurs within 30 days of the first TKA procedure ○ was previously randomized in this protocol ○ has a systemic active infection at the time of revision not including chronic viral infections such as HIV or hepatitis ○ has a remote-site skin infection at the time of revision ○ was tattooed on the area of the incision within 30 days prior to randomization ○ has known sensitivity to the study product components (drape and/or dressing materials in direct contact with the closed incision or skin) ○ has known sensitivity to silver ○ is currently enrolled in another investigational trial that requires additional interventions ○ is planned to be enrolled in another investigational trial that requires additional interventions at any time during the study

	
 ○ has localized skin cancer around the incision site ○ has a surgical incision that precludes placement of dressing ○ has a TKA revision resulting in a muscle flap ○ has a TKA revision resulting in the placement of a spacer ○ has an incision drainage and debridement procedure only ○ has a surgical incision closed with skin glue

STUDY EVALUATION/ VISIT SCHEDULE:
	
Subjects will be seen during Screening (no more than 30 days before TKA revision), at the TKA revision, at the weekly study treatment visits (a minimum of 5 days to a maximum number of days indicated in the Instruction for Use document for the selected dressing), the Midterm Follow-up visit (day 30 to 45), the Long Term Follow-up visit (day 90 to 104), or as initiated by either the Investigator or the subject (Unscheduled). All subjects will be followed for 90 days for outcomes regardless of the treatment received.


SAMPLE SIZE AND STATISTICAL METHODOLOGY:
	
The incidence rates of SSC are different for septic and aseptic revisions; the assumed SSC rate is 33% for septic and 6.9% for aseptic. This study plans to enroll at least 50% septic revisions overall. These enrollment rates lead to an assumed pooled SSC rate of 20% in the standard of care dressing arm.
 
Assuming an overall type 1 error rate of 0.05, with a two-sided hypothesis test, the study will have at least 80% power to detect a difference of 10% (50% reduction) in SSCs in the ciNPT arm with 199 subjects in each treatment arm, with one interim analysis at about 50% of the evaluable subjects for a total of 398 subjects using the likelihood ratio test. With an estimated 5%-10% loss, a non-binding interim analysis for superiority at approximately 50% of the evaluable subjects using O'Brien-Fleming method for monitoring boundaries, the planned sample size will be inflated for potential loss of follow-up for a total of 440 subjects.

SIGNATURE PAGE

Approved by: [Redacted] Date: [Redacted]
[Redacted]
Chief Medical Officer
KCI USA, an Acelity Company

Approved by: [Redacted] Date: [Redacted]
[Redacted]
Senior Director, Global Clinical Development
KCI USA, an Acelity Company

Approved by: [Redacted] Date: [Redacted]
[Redacted]
Interim Head, Global Clinical Safety
KCI USA, an Acelity Company

Approved by: [Redacted] Date: [Redacted]
[Redacted]
Vice President, Global Regulatory Affairs
KCI USA, an Acelity Company

Approved by: [Redacted] Date: [Redacted]
[Redacted]
Statistician, Global Biostatistics and Data Management
KCI USA, an Acelity Company

PRINCIPAL INVESTIGATOR ACKNOWLEDGEMENT OF PROTOCOL

I confirm that I have read the protocol entitled: “Post-market, Randomized, Open-Label, Multicenter, Study to Evaluate the Effectiveness of Closed Incision Negative Pressure Therapy versus Standard of Care Dressings in Reducing Surgical Site Complications in Subjects with Revision of a Failed Total Knee Arthroplasty (PROMISES)” Version 3.0, dated 6-Oct-18. I understand the protocol and agree to conduct the study according to the procedures therein in accordance with applicable local government regulations, institutional research policies and procedures, the Federal Drug Administration Code of Federal Regulations, the International Conference on Harmonisation principles of Good Clinical Practice, and in the spirit of the Declaration of Helsinki concerning medical research in humans.

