4.4. Subject Withdrawal or Termination

4.4.1. *Reasons for Withdrawal or Termination*

Subjects may withdraw from participation in the study at any time upon request.

The Investigator may choose to terminate participation of the subject from the study with or without their consent for any of the following reasons:

- Adverse events
- Noncompliance
- For any reason that may, in the opinion of the Investigator, negatively affect the safety or well-being of the subject.

An Investigator must terminate participation of a subject from the study for any of the reasons indicated in section 4.15.

4.4.2. *Handling of Withdrawal or Termination*

Every effort should be made to assess SSCs and adverse events prior to the subject withdrawal. If a subject does not return for a scheduled visit, every effort should be made to contact the subject.

For subjects who are lost to follow-up, the Investigator will make attempts to collect at least the vital status (e.g., whether the subject is alive) before formally withdrawing the subject from the study. Prior to considering a subject lost to follow-up at least two documented attempts should be made to contact the subject through all available routes, and a certified letter should be sent to the permanent address on file.

Once the subject withdraws from the study, no further study evaluations will be performed, and no additional data will be collected. The Investigator may retain and continue to use any data collected before withdrawal. The subject will not be replaced.

If for any reason the subject is withdrawn by the Investigator from this study, the Investigator will inform the subject and KCI.

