4.10.2. Application of Study Treatments

4.10.2.1. ciNPT

Subjects randomized to ciNPT will receive treatment for a duration consistent with the IFU document included with the selected Prevena™ Dressing but no shorter than five days post-surgery. Depending on the length of the incision, an appropriate Prevena™ Dressing will be used to cover the closed surgical incision, according to the instructions for use included with the product. Total treatment time should not exceed the maximum number days indicated in the IFU document included with the Prevena™ Dressing applied immediately following surgery.

For the delivery of negative pressure, an ActiV.A.C.® or Prevena Plus™ 125 Therapy Unit will be attached to the dressing tubing and ciNPT will be initiated in the operating room. The ActiV.A.C.® Unit must be set to 125mmHg of continuous negative pressure. If the dressing leaks and a seal cannot be maintained, replacement of the initial ciNPT dressing is acceptable and will be documented.

In the event that the Therapy Unit malfunctions, a replacement unit may be used. A dressing may also be replaced during the treatment period.

4.10.2.2. *Standard of Care (SOC)*

Subjects randomized to standard of care will have their closed surgical incision covered with the silver-impregnated dressing, Aquacel[®] Ag Surgical or other equivalent, up to the maximum number of days specified in the IFU but no shorter than five days post-surgery. Total treatment time should not exceed the maximum number days indicated in the IFU document included with the dressing applied immediately following surgery.

4.10.2.3. *Documentation*

The following information regarding the application of study treatments will be documented after the surgery:

- SOC
- Type of dressing applied
- ciNPT
 - Type of dressing applied (eg, Prevena Plus[™] Customizable[™] Dressing, Prevena[™] Peel & Place[™] Dressing)
- Type of therapy unit
 - ActiV.A.C.[®]
 - Prevena Plus[™] 125
- Replacement of the initial dressing to maintain the seal

4.10.3. **Removal of Study Treatments**

4.10.3.1. *ciNPT*

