All subjects must receive ciNPT for a duration consistent with the IFU document included with the selected Prevena[™] Dressing but no shorter than five days post-surgery. A maximum duration indicated in the IFU document of the Prevena[™] Dressing applied immediately following surgery is encouraged. The dressing should not be lifted or removed for reasons other than those related to the device such as initial malfunction or leak alarm.

At the end of the ciNPT treatment period, the dressing and unit are to be removed; re-application of the Prevena[™] dressing is prohibited after the treatment period. If continued drainage is determined by the Investigator's visual inspection of the incision at the time of dressing removal, an SSC event should be documented.

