4.10.3.3. Documentation

The following information regarding the application of study treatments will be documented after the surgery:

- Date of removal
- SOC only
- The number of dressing replacements
- Type of dressing (if any) applied after removal of study treatment
- ciNPT only
- Replacement of therapy unit
- Number and dates of dressing replacements (Prevena™ Peel & Place™ or Prevena Plus™ Customizable™)
- Type of dressing (if any) applied after removal of ciNPT

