4.15. Prohibited Procedures and Treatments

Subjects who undergo a subsequent surgery involving the initial TKA incision within 90 days must withdraw from the study.

Subjects who receive a subsequent TKA revision on the same knee within 90 days of the study revision must withdraw from the study prior to the procedure. Sites will record any SSCs that occur prior to the subsequent TKA revision and document the revision as the reason for the withdrawal from the study.

In the absence of an SSC, subjects receiving cross-over therapy after completing the original study treatment (ie, therapy from the arm in which the subject was not initially treated) must withdraw from the study.

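### Read literally, Protocol 4.15 withdraws a complication-free ciNPT subject who is given a silver dressing at removal, but not an SOC subject given the same dressing

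*Protocol*

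**What the plan says.** **SOC therapy.** The Synopsis and Protocol 3.2 give it as Aquacel Ag Surgical "or another equivalent silver-impregnated dressing, up to the maximum number of days specified in the IFU". Section 4.10.2.2 agrees: the incision is "covered with the silver-impregnated dressing, Aquacel[®] Ag Surgical or other equivalent".

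**Cross-over.** Protocol 4.15 covers a subject who has completed study treatment: "In the absence of an SSC, subjects receiving cross-over therapy after completing the original study treatment" are caught. Cross-over is glossed as "therapy from the arm in which the subject was not initially treated) must withdraw from the study". Section 4.4.1 makes termination by the investigator mandatory for any reason listed in 4.15.

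**Dressings after removal.** Section 4.10.3.3 records, for ciNPT, "Type of dressing (if any) applied after removal of ciNPT" and, for SOC, "Type of dressing (if any) applied after removal of study treatment". Neither item limits the type or mentions withdrawal. For ciNPT, 4.10.3.1 adds only that "re-application of the Prevena[™] dressing is prohibited after the treatment period".

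**After withdrawal.** Under 4.4.2, "no further study evaluations will be performed, and no additional data will be collected". An event-free subject with no assessment at or after day 90 is classed as incomplete follow-up (8.1.1). That subject is outside the mITT set (8.2) and outside the primary comparison (8.3.4).

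**Follow-up.** The visit schedule in the Synopsis and section 3.2 both state that every subject is followed for outcomes to day 90, whatever treatment was given.

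**The concern.** Aquacel Ag or an equivalent is the SOC study therapy. A ciNPT subject who receives it once ciNPT is complete has therefore, on the words of 4.15, received the other arm's therapy. The same dressing on an SOC subject is that subject's own arm's therapy, so the clause does not reach it. For SOC subjects the trigger is negative pressure therapy.

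The resulting exclusion falls on one arm and depends on outcome. SSCs are assessed at the visit where study treatment is removed (Protocol 5.1 and 5.2.4), and the clause applies only when no SSC is present. A ciNPT subject with an SSC by then stays and counts as an event. An event-free ciNPT subject given a silver cover leaves and counts as nothing.

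The SAP does not repair this. Section 7.3 imputes nothing for the primary endpoint. The ITT analysis in 8.5.1 is optional and gives no rule for subjects with incomplete follow-up.

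The related term alternative therapy is also undefined. It ends AE reporting, apart from SAEs judged related to study treatment (Protocol 7.7), and it excludes subjects from the mPP set (8.2). The same cover dressing could therefore affect safety capture and mPP membership.

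**Working it through.** **1. Who is caught by 4.15**

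| Subject, event-free at removal | Dressing placed at removal | Other arm's therapy? | Result under 4.15 |
|---|---|---|---|
| ciNPT | Aquacel Ag or equivalent | Yes, literally | Must withdraw |
| SOC | Aquacel Ag or equivalent | No | Not caught |
| SOC | Negative pressure dressing | Yes | Must withdraw |

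An SOC subject kept in a silver dressing beyond the IFU maximum departs from 4.10.2.2 and 4.10.3.2, but no withdrawal is attached to that.

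**2. The plan's own figure**

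Inputs from Protocol 8.4.2: SOC 20%, ciNPT 10%, two-sided 0.05, 80% power. With pooled variance:

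n = [1.960 × √(2 × 0.15 × 0.85) + 0.842 × √(0.20 × 0.80 + 0.10 × 0.90)]² / 0.10² = 199 per arm

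This reproduces the plan. At the final alpha of 0.048, power with 199 per arm is 79.5%.

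**3. Illustration of the effect**

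The documents do not give two inputs, which are assumed over a range:
- x: share of ciNPT subjects event-free at removal who are withdrawn for a silver dressing;
- f: share of ciNPT SSCs found by removal.

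Further assumptions: 199 per arm before these withdrawals, no other loss, an unstratified test at 0.048, and withdrawal unrelated to a subject's later SSC risk.

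With true ciNPT risk 10%, E = 19.9 events:
- retained ciNPT subjects: m = fE + (199 − fE)(1 − x)
- retained ciNPT events: e = fE + (1 − f)E(1 − x)
- power = Φ[(0.20 − e/m − 1.977·s₀)/s₁], where s₀ and s₁ are the pooled and unpooled standard errors of the difference.

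Example, x = 25%, f = 0.5:
- m = 9.95 + 189.05 × 0.75 = 151.7
- e = 9.95 + 9.95 × 0.75 = 17.4, so the rate is 11.5%
- pooled rate = (39.8 + 17.4)/(199 + 151.7) = 0.163, s₀ = 0.0398, s₁ = 0.0384
- power = Φ[(0.0852 − 0.0787)/0.0384] = Φ(0.17) = 57%

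Observed ciNPT rate and power:

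| x | f = 0 | f = 0.5 | f = 1 |
|---|---|---|---|
| 10% | 10.0%, 77% | 10.5%, 72% | 11.0%, 67% |
| 25% | 10.0%, 72% | 11.5%, 57% | 12.9%, 41% |
| 50% | 10.0%, 59% | 14.3%, 22% | 18.2%, 5% |

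At f = 0 the ciNPT rate is unbiased and only sample size is lost.

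**4. No true effect (20% v 20%)**

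At x = 25%, f = 0.5, the observed ciNPT rate is 22.6%. The chance of a significant result against ciNPT is 8.4%, where 2.4% is nominal. The chance of a significant result favouring ciNPT falls to 0.5%.

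**5. Loss allowance**

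The plan randomizes 440, or 220 per arm, which leaves 220 − 199 = 21 per arm for loss. At x = 10%, f = 0.5, about 189 × 0.10 = 19 subjects go, which fits if there is almost no other loss. At x = 25% about 45 to 50 go, which does not fit. Starting from 220 per arm with no other loss, power at x = 25% is 77%, 61% and 45% for f = 0, 0.5 and 1, against 83% with no such withdrawals.

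**The case against.** The strongest reply is that the forced exit is one reading and the rest of the Protocol points to a milder one. SOC therapy is a regimen: a dressing applied straight after surgery and worn for at least five days. A cover placed once ciNPT ends is arguably not that therapy. Section 4.10.3.3 expects a dressing after removal in both arms and attaches no consequence. The Synopsis and 3.2 keep every subject in follow-up to day 90. This much stands: no sentence says outright that a cover dressing is cross-over therapy. But no sentence exempts it either, 4.15 and 4.4.1 are mandatory in form, and the follow-up statement contradicts 4.15 without qualifying it. Across about 15 sites, either text could be followed.

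Some stronger readings are tempting, and the documents do not support them:
- *Any silver dressing is SOC therapy.* The text says Aquacel Ag Surgical or an equivalent, and equivalent is not defined.
- *Silver dressings after ciNPT are routine.* No frequency is given.
- *The ciNPT rate is certain to be inflated.* That needs some SSCs to be found by removal.

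It is also fair to say that, in the illustration, any bias runs against ciNPT, so it would not create a false claim of benefit. That depends on dressing choice being unrelated to later SSC risk, which the documents cannot confirm in an open-label trial.

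**Conclusion.** The point holds as an internal conflict with a one-arm consequence. Applied as written, 4.15 removes event-free ciNPT subjects given Aquacel Ag or an equivalent at removal, keeps ciNPT subjects who already have an SSC, and leaves SOC subjects in the same dressing untouched. It also contradicts the 90-day follow-up statement in the Synopsis and 3.2.

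Its size cannot be fixed from the documents. At an assumed 25% withdrawn, power falls from about 80% to between 72% and 41%, with 57% when half of SSCs are found by removal. The 50% row in the working shows the range and is not a forecast. No figure in the Protocol or SAP is wrong on this point, and the sample size reproduces. The change is worth making because it is cheap and protects the primary comparison.

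**What to change.** Reconcile Protocol 4.15 with the Synopsis visit schedule, 3.2, 4.10.3.3 and the mPP definition in 8.2:
- State in 4.15 whether a cover dressing without negative pressure, placed after study treatment, counts as cross-over or alternative therapy, and apply the answer equally to both arms.
- State that such a dressing does not end 90-day SSC outcome follow-up, so that these subjects stay in the mITT primary analysis.
- Limit the wording to dressings without negative pressure. The Prevena dressings themselves contain silver (Protocol Tables 1 and 2), so a general exemption for silver dressings would also release an SOC subject given Prevena.
- Keep recording the dressing type under 4.10.3.3.

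The choice of dressing stays with the sponsor. The cost is a sentence or two in 4.15, matching wording where the SAP refers to it, and a memo to sites. No new data items or subjects are needed.
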